11.3 Determination of Sample size

No formal sample size calculation has been performed: No recruitment or inclusion of patients that did not participated the previous phases (Randomized controlled trial and open label extension phase) is possible and the sample size of this study is therefore limited to a maximum, i.e. the number of patients ending the extension phase and being willing to participate.

12. Quality assurance and periodic monitoring

The investigator will maintain adequate and accurate records to enable the conduct of the study to be fully documented and the study data to be subsequently verified. These documents will be classified into two different categories: investigator's file, and subject clinical source documents.

August 09 2019 – Version 1.0

The investigator's file will contain the documents as per Good Clinical Practice and local regulations.

Regular monitoring will be performed by Hiruz CTU according to ICH-GCP. Data will be evaluated for compliance with the protocol and accuracy in relation to source documents. Following written standard operating procedures, the monitors will verify that the clinical trial is conducted and data are generated, documented and reported in compliance with the protocol, GCP and the applicable regulatory requirements. At least 3 monitoring visits are scheduled. An initiation visit, one routine visit and a final visit after the last patient had finished the study. The monitor will be working according to SOPs and will provide a monitoring report after each visit for the sponsor and the investigator. Depending on the quality of the data, additional monitoring visits will be necessary according to the sponsor's discretion.

More detailed information regarding the monitoring is described in the monitoring plan.

13. Indemnity insurance

An insurance with no fault responsibility has been foreseen by the sponsor in accordance with the Belgian law concerning experiments on humans, 7 May 2004..

14. Publication Policy

The results of this study will be reported and published at conferences and in peer-reviewed clinical journals. Authorship publications will follow the Uniform Requirement for Manuscripts Submitted to Biomedical Journals (International Committee of Medical Journal Editors, 2009), which states:

Authorship credit should be based on (1) substantial contributions to conception and design, acquisition of data, or analysis and interpretation of data; (2) drafting the article or revising it critically for important intellectual content; (3) final approval of the version to be published and (4) Agreement to be accountable for all aspects of the work in ensuring that questions related to the accuracy or integrity of any part of the work are appropriately investigated and resolved. Authors should meet conditions 1, 2, 3 and 4.

For further details, see http://www.icmje.org/recommendations/browse/roles-and-responsibilities/defining-the-role-of-authors-and-contributors.html.

15. Final Report

Within one year after the final completion of the study, a full final report will be written by the Chief Investigator and submitted to the central ethical committee and competent authority (via Hiruz CTU).

Part II : General part of the protocol

16. Independent Ethics Committee (IEC) / Institutional Review Bord (IRB)

This trial can only be undertaken after full approval of the protocol and addenda has been obtained from the IEC/IRB. This document must be dated and clearly identify the protocol, amendments (if any), the informed consent form and any applicable recruiting materials and subject compensation programs approved.

During the trial, the following documents will be sent to the IEC/IRB for their review:

- reports of adverse events that are serious, unexpected and associated with the investigational drug
- all protocol amendments and revised informed consent form (if any).

Amendments should not be implemented without prior review and documented approval / favorable opinion form the IEC/IRB except when necessary to eliminate an immediate hazard to trial subjects or when the change involves only logistical or administrative aspects of the trial.

Reports on, and reviews of the trial and its progress will be submitted to the IEC/IRB by the investigator at intervals stipulated in their guidelines.

At the end of the trial, the investigator will notify the IEC/IRB about the trial completion.

17. Competent Authority (CA)

This study must obtain approval from the competent authority (FAGG) prior to the start of the study. All protocol amendments will be notified to the competent authorities during the course of the trial.

Reports on safety, and reviews of the trial and its progress will be submitted to the CA by the sponsor (via Hiruz CTU) at intervals stipulated in their guidelines.

At the end of the trial, the sponsor will notify the CA (via Hiruz CTU) about the trial completion as per regulatory requirements.

18. Early termination

Early termination or suspension of the study or an investigational site may be necessary in case of major non-compliance, critical safety issues or premature trial discontinuation. This can occur at any time by the sponsor, principal investigator of the local site, EC or regulatory authority. In the event that the clinical investigation would be discontinued prematurely, all clinical investigation products will be retained, the terminating party shall justify its decision in writing and the sponsor will communicate (via Hiruz CTU) early termination, including the reason for early termination, to the EC and regulatory authority.

19. Protocol compliance

Prospective, planned deviations or waivers to the protocol are not allowed. Under emergency circumstances, deviations from the protocol to protect the rights, safety or well-being of human

August 09 2019 – Version 1.0

subjects may proceed without prior approval of the sponsor and the EC. Such deviations shall be documented and reported to Hiruz CTU by email ([contact]) and the EC as soon as possible. Accidental protocol deviations must be adequately documented and reported in the CRF on the protocol deviation log. In case accidental protocol deviations are considered as critical issues that significantly affect patient safety, data integrity and/or study conduct these should be reported to Hiruz CTU immediately by email ([contact]). Hiruz CTU will subsequently communicate and discuss this with the EC.

The following items will be documented on the protocol deviation log: date of deviation, description of deviation, actions taken and classification of deviation. Deviations will be classified as minor or major. A minor protocol deviation is a deviation that does not affect the safety, rights or well-being of subjects or the quality of their data. A major protocol deviation is a deviation that affects safety, rights or well-being of subjects or guality of their data.

Any deviation that potentially interferes with and/or affects the efficiency and/or quality conduct of the study will be discussed by the monitor with the PI and will be documented on the monitoring report including a proposed plan of action for resolution if applicable.

20. ICH/GCP guidelines

This trial will be conducted in accordance with the protocol, current ICH-GCP guidelines and applicable law(s).

Good Clinical Practice (GCP) is an international ethical and scientific quality standard for designing, conducting, recording and reporting trials that involve the participation of human subjects. Compliance with this standard provides public assurance that the rights, safety and well-being of trial subjects are protected, consistent with the principles that have their origin in the Declaration of Helsinki, and that the clinical trial data are credible.

21. Subject information and informed consent

Prior to entry in the trial, the investigator must explain to potential subjects the trial and the implication of participation. Subjects will be informed that their participation is voluntary and that they may withdraw consent to participate at any time. Participating subjects will be told that their records may be accessed by competent authorities and by authorized persons without violating the confidentiality of the subject, to the extent permitted by the applicable law(s) and/or regulations. By signing the Informed Consent Form (ICF), the subjects are authorizing such access.

After this explanation and before entry to the trial, written, dated and signed informed consent should be obtained from the subject. The ICF should be provided in a language sufficiently understood by the subject. Subjects must be given the opportunity to ask questions.

The subject will be given sufficient time to read the ICF and to ask additional questions. After this explanation and before entry to the trial, consent should be appropriately recorded by means of the subject's dated signature or the signature of an independent witness who certifies the subject's consent in writing. After having obtained the consent, a copy of the ICF must be given to the subject.

In case the subject is unable to read, an impartial witness must attest the informed consent.

August 09 2019 – Version 1.0

22. Case Report Forms

The source documents are to be completed at the time of the subject's visit. The CRFs are to be completed within reasonable time after the subject's visit.

Annex I

IMP label

EudraCT N°: 2019-003570-11 TRIAL subject ID nr°: _____ Initialen: _____ Datum visite: _____ ENKEL VOOR STUDIEGEBRUIK Gebruiksaanwijzing: eenmaal per week een in leidingwater opgeloste bruistablet – 12 bruistabletten Elke bruistablet bevat 70mg alendronaat - Voor oraal gebruik - Buiten het zicht en bereik van kinderen houden – Bewaar in de originele verpakking ter bescherming tegen vocht. UNIQUEMENT POUR UTILISATION DE L'ESSAI CLINIQUE Mode d'emploi : un comprimé effervescent une fois par semaine, sous forme de solution buvable – 12 comprimés effervescents - Chaque comprimé contient d'alendronate 70mg - Voie orale - Tenir hors de la vue et de la portée des enfants - A conserver dans l'emballage extérieur d'origine, à l'abri de l'humidité. NUR STUDIENGEBRAUCH KLINISCHER Gebrauchsanweizung: Nehmen Sie einmal pro Woche eine in Leitungswasser gelöste Brausetablette ein. - 12 Brausetabletten - Jede Brausetablette enthält 70mg Alendronat - oraler Einnahme -Artznemittel für Kinder unzugänglich aufbewahren - In der Originalverpackung aufbewahren, um den Inhalt vor Feuchtigkeit zu schützen Exp:dayMONTHyear [name] [contact] SPONSOR: UZ GENT [name]

# 2. Background and rationale of the study

### 2.1 Background

Denosumab, anti-RANK ligand therapy discontinuation, is associated with a rebound in bone turnover and loss of bone mineral density. These changes result in increased fracture incidence in patients with postmenopausal osteoporosis back to background levels. Amongst the patients that presented with vertebral fractures after treatment discontinuation, there is a slightly higher incidence of multiple vertebral fractures in patients discontinuing Prolia versus those that discontinued placebo.

In our study 'RANKL-blockade for the treatment of erosive hand osteoarthritis (OA) of interphalangeal finger joints' (EudraCT number: 2015-003223-53; Protocolnumber: AGO/2015/008) patients are randomized to placebo or denosumab (60 mg/Q3M) for 1 year followed by a two-year open label extension in which all subjects receive denosumab (60 mg/Q3M) (1). Also in this non-osteoporotic population, increases in bone turnover are expected as soon as patients end study participation.

It is currently recommended that other anti-resorptive therapy may is warranted after Denosumab discontinuation. Several studies describe the use of oral alendronate after denosumab therapy to maintain bone mineral density. However, gastro-intestinal upset and tolerability, as well as difficulty swallowing pills may limit oral alendronate use. In the current study proposal we want to examine the use of effervescent alendronate (Steovess/Binosto) in subjects that completed our hand erosive osteoarthritis study and therefore discontinued denosumab 60 mg/Q3M.We hypothesize that Steovess/Binosto will be able to maintain bone turnover markers within the reference range thereby reducing the likelihood of bone turnover associated changes.

In erosive hand OA, destructive erosive changes, followed by remodelling is key characteristic for the disease. As in inflammatory rheumatic diseases, the RANKL pathway appears to be involved in the pathogenesis and hence, a therapeutic role of its blockade has been studied in the study described above. It is unknown if a potential rebound effect in bone turnover might also be associated with a rebound in erosive destructive progression at the subchondral bone.

## 2.2 Hypothesis and objectives

It is hypothesized that effervescent alendronate will be able to maintain bone turnover markers within the reference range thereby reducing the likelihood of bone turnover associated changes, after discontinuation of denosumab treatment in a non-osteoporotic population.

The **primary objective** of this study is to assess the effect of effervescent alendronate after denosumab discontinuation on the change in bone turnover markers after 48 weeks in a non-osteoporotic population and to assess if there is a difference between using oral alendronate after 24 or 48 weeks.

The **secondary objective** is to evaluate the effect of effervescent alendronate after denosumab discontinuation on bone mineral density in this non-osteoporotic population and assess difference in oral alendronate therapy for 24 versus 48 weeks.

**Exploratory objectives** are to study the effect of oral alendronate therapy after denosumab discontinuation on erosive destructive progression at the subchondral bone in erosive hand OA patients and to assess the effect of oral alendronate on their hand pain scores.

#### 2.3 Study design

This is a monocentric randomized study to investigate the effect of effervescent alendronate on bone turnover markers after denosumab discontinuation. At the earliest three months but no later than

four months after the last denosumab injection, 40 subjects will be randomized to effervescent alendronate administered for either 24 (n=20) or 48 weeks (n=20). The randomization was performed by a randomization manager. The total treatment duration per subject is 48 weeks.

## 3. Study population

## 3.1 Inclusion and exclusion criteria

Cfr Protocol (version 1.0 dd 09/08/2019)

### 3.1.1. Inclusion criteria

A subject will be eligible for study participation if he/she meets the following criteria:

- Subjects must have completed the 48 weeks of the randomised placebo-controlled study phase followed by the 96 weeks open label denosumab 60 mg SC every 3 months phase. (EudraCT number: 2015-003223-53)
- Last denosumab injection less than four months ago
- Able and willing to give written informed consent and to comply with the requirements of the study protocol

### 3.1.2 Exclusion criteria

A subject will be excluded from the study if he/she meets any of the following criteria:

- Patients with clinically significant hypersensitivity to any of the components of effervescent alendronate.
- Patient who is pregnant or planning pregnancy
- Female subjects who are breast-feeding.
- History of osteonecrosis of the jaw, and/or recent (within 3 months) tooth extraction or other unhealed dental surgery; or planned invasive dental work during the study
- Subject has any kind of disorder that compromises the ability of the subject to give written informed consent and/or to comply with study procedures
- Hypocalcaemia.
- Oesophageal disease, gastritis, duodenitis, ulcers, or with a recent history (within the previous year) of major gastro-intestinal disease such as peptic ulcer, or active gastro-intestinal bleeding, or surgery of the upper gastro-intestinal tract other than pyloroplasty.
- Abnormalities of the oesophagus and other factors which delay oesophageal emptying such as stricture or achalasia.
- Inability to stand or sit upright for at least 30 minutes.

### 3.2 Data sets analysed

### 3.2.1 Safety analysis

The safety dataset includes all patients who received at least 1 dose of effervescent alendronate. This dataset will be used to summarize adverse events and safety analysis.

### 3.2.2 Full analysis dataset

The full analysis set will include all patients who are randomly allocated to a treatment group and received at least 1 dose of effervescent alendronate.

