4.5. Administration way

Effervescent alendronate 70 mg should only be taken upon arising for the day dissolved in half a glass of plain water (not less than 120 ml or 4.2 fl.oz.). Dissolving the tablet in water yields a buffered solution of pH 4.8 - 5.4. The buffered solution should be drunk, once the fizzing has subsided and the effervescent tablet has completely dissolved to give a clear, colourless, buffered solution, followed by at least 30 ml (one sixth of a glass) of plain water. Additional plain water may be taken. Patients should not swallow the undissolved effervescent tablet, should not chew the effervescent tablet or allow the effervescent tablet to dissolve in their mouths because of the risk for oropharyngeal irritation. Patients should not lie down for at least 30 minutes after taking effervescent alendronate 70 mg.

Steovess will be distributed during study visits. Subjects should take one 70 mg effervescent tablet once weekly at home. Patients should be instructed that if they miss a dose of alendronate 70 mg, they should take one effervescent tablet on the morning after they remember. They should not take two effervescent tablets on the same day but should return to taking one effervescent tablet once a week, as originally scheduled on their chosen day.

August 09 2019 – Version 1.0

Alendronate 70 mg must be taken at least 30 minutes before the first food, beverage, or medicinal product of the day with plain water only. Other beverages (including mineral water), food and some medicinal products are likely to reduce the absorption of alendronate.

Patients are requested not to take any study medication on the morning of a planned visit (week 12, week 24 or week 48): this accounts for the study medication (Steovess) and the calcium/ vitamine D supplements.

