### 3.2.3 Protocol violations and handling of missing data

Major protocol violations thought to affect the assessment of efficacy of the study drug will be considered. The following situations will be considered as major protocol violations:

- Patients who withdrew or were withdrawn from the study
- Patients having received less than 50% of the study medication

Data of withdrawn patients will be included up until the moment of withdrawal. If measurements are recorded after withdrawal when not completed the appropriate duration of active treatment, these measurements will be considered as missing. For analysis of the primary endpoint, all data available will be used for analysis and imputation of missing values will be performed. More specifically, drop-outs will be considered as non-responders in all outcome measures (primary and secondary endpoints where linear mixed models will be used, and in the number of patients exceeding reference ranges). Only in the analyses of percentage changes of BMD and percentage of patients with a BMD loss higher than the least significant change, drop-outs will be considered as true drop-outs.

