### 5.2 Primary outcome analysis

The primary outcome analysis will be performed in an intention to treat approach, where drop-outs were considered as non-responders. Changes in bone turnover marker levels will be analysed with a linear mixed model. Data from all available time points will be used. Normal distribution will be checked and data transformations will be performed if necessary if assumptions of normality aren't reached. P-values and estimated marginal means will be calculated at different time points.

All analyses will be performed with a two-sided p-value. A p-value below 0.05 (p<0.05) will be considered statistically significant.

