#### 5.3 Secondary outcome analysis

Bone density measures will be analysed in an intention to treat approach, using a linear mixed model. Data from all available time points will be used. Normal distribution will be checked and data transformations will be performed if necessary if assumptions of normality are not reached. P-values and estimated marginal means will be calculated at different time points.

In addition, percentage changes in BMD and the percentage of patients with a BMD loss higher than the least significant change (LSC), which represents the smallest difference between successive measurements of BMD that can be considered a real change, will calculated. Here no intention to treat approach will be used.

The number of patients exceeding reference ranges will be calculated with an intention to treat approach, where drop-outs will be considered as non-responders. A Fisher's exact test was used to assess differences in patient numbers exceeding reference ranges between both treatment groups.

All statistical tests were two-tailed and a p-value below 0.05 ( $\alpha$ ) was considered statistically significant.

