### 5.4 Exploratory outcome measure analysis

Hand pain scores will be analysed using an intention to treat approach, using a linear mixed model. Data from all available time points will be used. Normal distribution will be checked and data transformations will be performed if necessary if assumptions of normality are not reached. P-values and estimated marginal means will be calculated at different time points. Changes in new erosive joint count on radiographs, scored using the Verbruggen and Veys anatomical phase scoring system (2) and hand pain scores, measured using a NRS pain scale at week 48. The number and percentage of joints in each radiographical phase (N, S, J, E and R phase) will be reported. The total number and percentage of pre-erosive joints (N,S and J phase) progressing to an erosive phase during the trial will also be reported.

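### The only efficacy set in the SAP requires at least one dose, so a randomised patient who never starts is left out of analyses labelled intention to treat

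*SAP*

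**What the plan says.** SAP 3.2.2 puts a patient in the full analysis set only if "randomly allocated to a treatment group and received at least 1 dose of effervescent alendronate". SAP 3.2.1 sets the same dosing condition for safety: "The safety dataset includes all patients who received at least 1 dose of effervescent alendronate". The available SAP text defines no other analysis set.

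The analysis sections use a wider label:
- SAP 5.2, turnover markers: "The primary outcome analysis will be performed in an intention to treat approach, where drop-outs were considered as non-responders".
- SAP 5.3, bone density: "Bone density measures will be analysed in an intention to treat approach, using a linear mixed model".
- SAP 5.3, reference-range counts: "The number of patients exceeding reference ranges will be calculated with an intention to treat approach", followed by Fisher's exact test.
- SAP 5.4, hand pain: "Hand pain scores will be analysed using an intention to treat approach, using a linear mixed model".

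For missing data, SAP 3.2.3 states that "drop-outs will be considered as non-responders in all outcome measures". It exempts only the percentage changes in BMD and the share of patients losing more than the least significant change.

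On conduct, protocol 4.1 makes the treatment open label. Protocol 5.1 has the tablets provided after randomisation at the baseline visit. Protocol 4.5 has them taken on rising: "Subjects should take one 70 mg effervescent tablet once weekly at home". Protocol 4.9 asks patients to log their own intake.

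**The concern.** Intention to treat ordinarily means that every randomised patient is analysed in the allocated arm. The one-dose condition is an exclusion applied after randomisation. It does little harm where the decision to start cannot depend on the arm, as under blinding. That protection is absent here, because a patient can learn whether the allocation is 24 or 48 weeks before deciding whether to take the first tablet.

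The drop-out rule, which is meant to count departures as failures, does not reach these patients because they are outside the set to which it applies. Two patients who behave almost alike, one stopping after a single tablet and one before it, are therefore handled in opposite ways. With 20 patients per arm, a single such case is visible in the result.

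**Working it through.** **Text check**

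| Patient | In the full analysis set (SAP 3.2.2)? | Handling of the in-range count (SAP 3.2.3, 5.3) |
|---|---|---|
| Takes one tablet, then drops out | Yes | Non-responder |
| Randomised, takes no tablet | No | Not counted |
| Same patient, all randomised analysed | Yes | Non-responder, if treated as a drop-out |

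No other section resolves the mismatch. Protocol 11.1 plans a per-protocol analysis of week-48 completers, so it does not supply an all-randomised set either.

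**Scale**

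The plan has no figure to reproduce: protocol 11.3 reports no sample size calculation, and neither document gives an expected in-range rate or a number of non-starters. The counts below are assumptions chosen to show scale.

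Inputs from the documents: 20 randomised per arm (protocol 3.1, SAP 2.3); two-sided Fisher's exact test at 0.05 (SAP 5.3). Each patient is 1/20 = 5% of an arm.

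Let arm A have a patients in range out of n, and arm B have b out of m. With F = (n − a) + (m − b) failures in total, the probability of x failures in arm A is

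P(x) = C(n, x) · C(m, F − x) / C(n + m, F).

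The two-sided p-value is the sum of all P(x) that do not exceed the probability of the observed table.

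Suppose k patients in arm A never start. Analysing all randomised patients keeps them as failures, so n = 20. The SAP 3.2.2 set removes them, so n = 20 − k. The number in range, a, is the same either way.

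| Assumed in range, all randomised | p | SAP 3.2.2 set, k = 1 | p | SAP 3.2.2 set, k = 2 | p |
|---|---|---|---|---|---|
| 18/20 vs 12/20 | 0.065 | 18/19 vs 12/20 | 0.020 | 18/18 vs 12/20 | 0.0035 |
| 18/20 vs 14/20 | 0.235 | 18/19 vs 14/20 | 0.091 | 18/18 vs 14/20 | 0.021 |
| 18/20 vs 16/20 | 0.66 | 18/19 vs 16/20 | 0.34 | 18/18 vs 16/20 | 0.11 |

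In the first row one exclusion raises the rate in arm A from 18/20 = 90.0% to 18/19 = 94.7% and crosses 0.05. In the second row one exclusion does not cross; it would take two, meaning that every failure in that arm was a non-starter. In the third row even two do not.

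Exclusion from the lower arm acts the other way: 18/20 vs 12/18 gives p = 0.117, against 0.065 with all randomised.

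**How often a non-starter might occur**

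If each patient independently fails to start with probability q, the chance of at least one among 40 is 1 − (1 − q)^40. Assumed q of 1%, 2.5% and 5% give 33%, 64% and 87%. The documents give no basis for choosing q.

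**The case against.** The strongest defence is that allocation gives little reason to refuse the first tablet. Both arms take the same drug once weekly and differ only in planned duration, so nothing separates them until week 24. Patients have completed 48 + 96 weeks of the earlier study, must be willing to comply, and may stop at any time. Someone unwilling to take 48 weeks of treatment could start and stop later, and SAP 3.2.3 would then count that patient as a failure. This stands: differential non-starting is possible but probably rare, and non-starting of any kind may be zero.

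Two links are inferences. Protocol 4.5 describes weekly intake at home in general, and no section describes the first dose. Home intake is the natural reading, given dosing on rising and dispensing after randomisation, but it is not stated. Nor does the SAP say that the intention-to-treat analyses use the set in 3.2.2; that follows only because no other efficacy set is defined. If the sponsor meant all randomised patients, 3.2.2 still needs correcting, because an analyst could not tell which population to use.

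The p-values above concern the in-range counts. These are secondary in the SAP (4.2), although in-range CTx-I at week 48 is the primary endpoint in protocol section 2. The SAP's own primary analysis is a mixed model on continuous markers, and no effect on it has been shown here. The threshold crossing also depends on a split close to 0.05.

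**Conclusion.** The one-dose condition in SAP 3.2.2 contradicts the intention-to-treat label in SAP 5.2 to 5.4 and leaves never-dosed patients outside the drop-out rule. It should be corrected, at moderate priority.

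The size depends on facts the documents do not give. If every patient starts, the two sets are identical. If one does not, 5% of an arm is removed, which can matter for a borderline in-range comparison and usually not otherwise. This rests on the full analysis set being the population for the intention-to-treat analyses, and on patients learning their allocation before the first tablet.

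A reader might infer that the condition biases the trial towards one duration, or that it undermines the SAP's primary analysis. The documents support neither. The exclusion can favour either arm, no non-starters are reported, treatment is the same in both arms for 24 weeks, and the worked figures do not bear on the mixed model.

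**What to change.** In SAP 3.2.2, define the full analysis set as all randomised patients, analysed in the arm to which they were allocated. Keep the one-dose condition in SAP 3.2.1 for safety only. Then add:
- In the in-range (Fisher) analysis, never-dosed patients count as non-responders.
- In the mixed models, their available measurements, at least baseline, are included. The non-responder rule alone does not settle this, because the SAP gives no value for a non-responder on a continuous marker.
- The number never dosed is reported by arm.

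The core change is one sentence, with three short additions, and needs no new data. Estimates may shift slightly in either direction if anyone never started; otherwise nothing changes and the intention-to-treat label becomes accurate.
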